8.1.4.16 Tachyarrhythmia episodes

During the course of the study the following tachyarrhythmia episodes have to be recorded, analyzed and evaluated on the tachyarrhythmia episode form:

- All episodes detected in the VT-1, VT-2 or VF-zone
- All episodes with attempted and/or delivered therapies (ATP and/or shock)
- The first new and last two AF and/or SVT episodes between two follow-ups.

The appropriateness of the episode detection and the success of the delivered ATPs and/or shocks to terminate the episode will be evaluated. The corresponding IEGM should be stored by opening it manually and provided to the sponsor (see section 8.1.4.19). In case of new onset of AF, the investigator will be asked if the episode was detected by Home Monitoring prior to the follow-up.

8.1.4.17 Assessment of statistic for ATP optimization

If ATP optimization was programmed 'ON' (optional), the investigator will be asked to assess the statistics for ATP optimization at the 12-month follow-up for patients that experienced tachyarrhythmia episodes treated with ATP in the course of the study.

The investigator will be asked to assess the comprehensibility and the usefulness in the categories "Very good/good/adequate/poor/very poor".

The eCRF may be accepted as source document for the assessment ATP statistics.

8.1.4.18 RV/LV Capture Control at permanent DDI mode

Home Monitoring data will be analyzed to identify any patients in permanent DDI mode in whom capture control is activated in at least one of the ventricular channels (RV, LV and/or LV2). The AE database will be searched for Adverse Device Effects related to loss of capture that occurred in these patients.

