4.3 Model name including software version and accessories

Except for the CRT-DX models and the Rivacor 3 series, all commercially available Acticor and Rivacor devices and Plexa ProMRI S DX models can be used in this study. The exact device names and catalogue numbers are listed in Table 1 and

Table 2. Participating sites located outside the CE area will only use those devices which received market or study approval by the respective regulatory institution according to the national regulations.

Table 1: Eligible devices of the Cor Family

Device name	Catalogue number
Acticor 7 VR-T	
Acticor 7 VR-T DX	
Acticor 7 DR-T	
Acticor 7 HF-T	
Acticor 7 HF-T QP	
Rivacor 7 VR-T	
Rivacor 7 VR-T DX	

Device name	Catalogue number
Rivacor 7 DR-T	[REDACTED]
Rivacor 7 HF-T	[REDACTED]
Rivacor 7 HF-T QP	[REDACTED]
Rivacor 5 VR-T	[REDACTED]
Rivacor 5 VR-T DX	[REDACTED]
Rivacor 5 DR-T	[REDACTED]
Rivacor 5 HF-T	[REDACTED]
Rivacor 5 HF-T QP	[REDACTED]

Table 2: Eligible Plexa S DX leads

Device name	Catalogue number
Plexa ProMRI S DX 65/15	[REDACTED]
Plexa ProMRI S DX 65/17	[REDACTED]

During this clinical investigation, the devices under investigation are to be used with the following components:

- Any commercially available bipolar atrial lead providing IS-1 connection, preferably a BIOTRONIK lead (or no atrial lead in case single chamber device system is implanted).
- Any commercially available ICD lead providing a DF4 connector, preferably a BIOTRONIK lead. (For VR-T DX devices the Plexa ProMRI S DX lead is mandatory.)
- For CRT-D: Any commercially available left ventricular lead providing an IS-1 (HF-T) or IS4 (HF-T QP) connector, preferably a BIOTRONIK lead. If a HF-T QP device is implanted, Sentus ProMRI OTW QP lead is recommended.
- BIOTRONIK accessories are recommended, e.g. Selectra catheter
- BIOTRONIK Renamic or successor devices
- BIOTRONIK programmer software PSW 1801.A/4 and subsequent versions
- BIOTRONIK Renamic PSA module, PSA patient cables and patient adapters, e.g. BIOTRONIK IS4/DF4 adapter are recommended
- BIOTRONIK CardioMessenger Smart or successor devices
- BIOTRONIK Home Monitoring Service Center (HMSC) 3 and subsequent versions

Within the frame of this clinical investigation, all used devices carry a CE mark. Participating sites located outside the CE area will only use these devices after market or study approval by the respective regulatory institution according to the national regulations.

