4.7.1.7 RV/LV CC at permanent DDI mode

Capture control (CC) algorithms are used in all channels to automatically monitor pacing thresholds and adapt the pacing amplitudes accordingly. Thus it is possible to ensure that the stimulation amplitude always is set to small but effective values but also never falls below the minimum value required for the patient. Temporal threshold changes are thus reflected in a safe and effective manner.

The pacemaker modes for RV/LV CC could not be combined with DDI(R) mode in the previous ICD families. However, nowadays DDI(R) mode is used more frequently as permanent mode in patients with persistent or paroxysmal AT/AF heart rhythm, than in the past. Thus the Cor Family ICDs will complete the pacemaker modes by DDI(R) mode in combination with RV/LV CC.

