8.1.4.15 Lead measurements with Renamic programmer at implantation and each follow-up

The system performance, i.e. appropriate sensing and pacing is evaluated at the end of the implantation procedure and **at the end** of each follow-up by either manually or automatically triggered lead measurements. For this purpose the investigator performs the threshold tests, determines pacing impedance and painless shock impedance and performs P/R-wave amplitude measurements in all available channels (in DX leads also sensing measurements in the atrial channel). In the RA and RV the pulse width must be 0.4 ms, in the LV any pulse width can be chosen. For CRT-D patients measurement of LV pacing vectors with the Automatic LV VectorOpt feature is **mandatory**, either at Pre-hospital discharge or at time of the 3-month follow-up. Pacing polarities of the LV channel must be documented. The type of programmer is also documented.

If no manual measurements were performed during the on-site follow-up, the values which were automatically measured by the device the previous day are acceptable.

The investigator is asked to assess the sensing and pacing performance at the end of each follow-up (including storing of an IEGM snapshot): The sensing of the lead will be assessed as "adequate" (= the device sensed the current rhythm correctly) or "inadequate". In the ventricles the additional option "no intrinsic rhythm" (= patient is fully paced) is available to describe if an evaluation of sensing is not possible. In case the sensing is considered inadequate, the reason "oversensing", "undersensing", "not measurable" (= quality/content of IEGM does not allow any discrimination if senses are correct (e.g. lead dislodgement)) or "other" will be determined. The pacing of the lead will be assessed as "adequate" (=successful stimulation) or "inadequate". In case the pacing is considered inadequate, the reason for the evaluation is required. Possible options are "non-capture" (= no evidence of depolarization after pacing), "no output" (= failure to pace: impulses are generated by the device but is not transferred to the myocardium), "not measurable" (= quality/content of IEGM does not allow any discrimination if stimulation is successful) or "other".

At the end of the on-site follow-up procedure the full follow-up data set shall be provided to the sponsor and will be used for source data verification (see section 8.1.4.19).

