18.1 Definition of adverse events

An AE is defined* as any untoward medical occurrence, unintended disease or injury, or untoward clinical signs (including abnormal laboratory findings) in subjects, users or other persons whether or not related to the investigational device. This includes:

- Events related to the investigational device or the comparator
- Events related to the procedures involved
- For users or other persons, this definition is restricted to events related to the investigational devices.

*see ISO 14155 3.2

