18.3 Definition of device deficiency

Device deficiency (DD)* is defined as inadequacy of a device with respect to its identity, quality, durability, reliability, safety, or performance, including malfunctions, use errors and inadequate labeling.

*see ISO 14155 3.15

DDs of the investigational device shall be documented throughout the study. DDs which caused an adverse event are reported on the respective adverse event form. In case the DD did not cause an adverse event the provided DD form shall be used to document this "non-medical" event.

If a DD could have led to a SADE,

- if either suitable action had not been taken,
- if intervention had not been made, or
- if circumstances had been less fortunate,
- the DD is classified as an DD with an SADE potential.

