8.2.9 RV/LV active capture control at permanent DDI mode

CIP chapter 8.1.4.18 RV/LV Capture Control at permanent DDI mode

Home Monitoring data will be analyzed to identify any patients in permanent DDI mode in whom capture control is activated in at least one of the ventricular channels (RV, LV and/or LV2). The AE database will be searched for Adverse Device Effects related to loss of capture that occurred in these patients.

Information for the CIR will be based on the Vigilance AE report and on separate Home Monitoring analyses.

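### The one outcome specified for RV/LV capture control in permanent DDI mode is a search for Adverse Device Effects, which leaves out loss of capture attributed only to a lead and is not linked to device deficiencies or visit findings of inadequate pacing

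*Protocol*

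**What the plan says.** CIP 4.7.1.7 explains that capture control follows the pacing threshold so that output does not fall below what the patient needs. Earlier ICD families could not combine it with DDI(R): "Thus the Cor Family ICDs will complete the pacemaker modes by DDI(R) mode in combination with RV/LV CC". CIP 7.5.1 lists the combination as further data of interest.

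The method is in CIP 8.1.4.18. First, "Home Monitoring data will be analyzed to identify any patients in permanent DDI mode" with capture control active in at least one ventricular channel. Then: "The AE database will be searched for Adverse Device Effects related to loss of capture that occurred in these patients". SAP 8.2.9 repeats this and adds one sentence: "Information for the CIR will be based on the Vigilance AE report and on separate Home Monitoring analyses". It names no variable, table, denominator or rate.

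Loss of capture can also be recorded in two other places.
- Device deficiencies (CIP 18.3): "In case the DD did not cause an adverse event the provided DD form shall be used to document this" event.
- The pacing assessment at every visit (CIP 8.1.4.15): "In case the pacing is considered inadequate, the reason for the evaluation is required". Non-capture is one of the reasons offered.

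**The concern.** Capture control exists to keep pacing effective, so its failure shows up as loss of capture. The search keeps only those events that count as ADEs, that is, AEs related to an investigational device (CIP 18.2). When a threshold rises at the lead and output does not follow, an investigator may reasonably attribute the event to the lead. That is also the situation the algorithm is meant to handle.

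A report of no ADE related to loss of capture, with no number of patients beside it, would be read as support for the feature in this mode. The search as written cannot carry that reading, because it leaves out one class of relevant event by rule and does not consult two records where others may sit.

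**Working it through.** The plan gives no figure for this check, so the main work is to trace the definitions. The arithmetic at the end is illustrative.

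**1. Who is concerned.** DDI is a dual-chamber pacing mode (CIP list of abbreviations), so it concerns DR-T, HF-T and HF-T QP. From the planned distribution in CIP 8.2.4: 15 + 15 + 52 = 82 of 127 devices. The number in permanent DDI with capture control active is not stated.

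**2. Which leads are investigational.** CIP 4.1 names the Cor Family generators and the Plexa S DX lead. CIP 4.3 makes Plexa S DX mandatory only for VR-T DX. For other systems the RV lead is "Any commercially available ICD lead providing a DF4 connector, preferably a BIOTRONIK lead", and the LV lead is likewise any commercial lead with the right connector. CIP 8.1.5 calls both freely selectable, with one quadripolar LV lead recommended for HF-T QP.

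**3. Where each kind of record goes.**

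| Record | Export (SAP 5.9) | In the CIP 8.1.4.18 search? | Reported elsewhere? |
|---|---|---|---|
| AE, loss of capture, related to the generator | adverse_event | Yes | Vigilance AE report |
| AE, loss of capture, attributed only to a non-investigational lead | adverse_event | No: not an ADE | Vigilance AE report, not linked to these patients |
| Malfunction without an AE | device_deficiency | Not named | Vigilance AE report (SAP 8.2.12), not linked |
| Inadequate RV or LV pacing at a visit | lead_measurement | Not named | SAP 8.2.5, all patients together |

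CIP 11.9 plans no repeat of analyses in subsets, so the last three rows are never set against the DDI patients. The primary endpoint does not fill the gap, because events corrected non-invasively, for example by reprogramming, do not count (CIP 18.5.1). The AE form records relation to MultiPole Pacing and to CRT AutoAdapt (CIP 8.1.4.22) but has no such item for capture control.

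**4. State of the visit data.** In SAP 8.2.5 the RV adequacy row carries DURAPCAD, which is also the RA variable. The SAP's reason list has exit block at maximum output and 'other', but no separate non-capture value like the one in CIP 8.1.4.15.

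**5. Size (assumptions marked).** CIP Table 6 places RV and LV loss of capture each at 1 to 10 per 100 patients. Those are literature rates for ICD and CRT systems in general, not for patients with capture control active. Assume 10 to 20 patients in the set.
- Expected events per chamber: 10 × 0.01 = 0.1 to 20 × 0.10 = 2.
- Exact two-sided 95% upper limit after no event, 1 − 0.025^(1/n): 30.8% for n = 10, 21.8% for n = 15, 16.8% for n = 20.
- Chance of finding no event, (1 − p·c)^n, with n = 15, p = 5% and c the share of events coded as ADEs: 46% for c = 1, 68% for c = 0.5, 83% for c = 0.25. All three inputs are assumptions.

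**The case against.** Several counter-arguments are sound.

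- *Symptom-free events are reportable.* A reader might infer that the definitions exclude them. They do not. An AE is "any untoward medical occurrence, unintended disease or injury, or untoward clinical signs (including abnormal laboratory findings", with no symptom condition, and Table 6 lists loss of capture as an anticipated AE. What remains is a risk that such findings are recorded elsewhere.
- *Lead-attributed events are not all lost.* A weak relation with another device as an alternative cause is still classed as possible, and so is relatedness that cannot be assessed (CIP 18.2.1). A Plexa S DX lead is itself investigational, and CIP section 3 says it can be connected to HF-T and HF-T QP devices. Only events attributed to a non-investigational lead alone fall outside.
- *There is other evaluation.* Thresholds and pacing adequacy are reported at each visit for everyone (SAP 8.2.4, 8.2.5). Device deficiencies reach the report through the same Vigilance source that SAP 8.2.9 names. The SAP also mentions Home Monitoring analyses, though without content. It would be wrong to say the feature gets no other evaluation. None of this, however, is specified for the DDI patients.
- *The visit record is imperfect.* Pacing is assessed at the end of the visit, whereas reprogramming is listed first (CIP 9.5), so a corrected failure may be scored adequate. Exit block at maximum output does not show a failure of the algorithm. Both points limit the visit data; neither makes them useless.
- *This is exploratory.* The item is further data of interest without a hypothesis (SAP 8.6), and restricting a device check to device-related events favours specificity. That argues for a modest change, not for leaving the rule as it is.

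**Conclusion.** The point holds in a limited form. The only outcome specified for this feature is an ADE search without a denominator. It drops, by rule, loss of capture attributed only to a non-investigational lead, including cases where output did not follow a threshold change. It is not linked to the device deficiencies and visit findings where silent cases may be recorded.

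A reader might go further and expect a clean result because of the ADE rule. The documents do not support that. The number of patients is unknown, and in the illustration with 15 patients and a 5% event rate, no event would be found 46% of the time even if every event were caught. The filter adds to that chance by an amount that cannot be fixed from the documents. Small numbers are a further reason to show the denominator. The conclusion rests on the definitions and data flow, not on the assumed rates. The change is worth making but has no bearing on the primary endpoint.

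**What to change.** Amend SAP 8.2.9. For the patients identified by Home Monitoring as in permanent DDI mode with ventricular capture control active, list:

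- (a) all AEs of loss of capture whatever their device relation, with the attributed cause;
- (b) device deficiencies involving loss of capture;
- (c) visit records of inadequate RV or LV pacing with reason non-capture or 'other', using the RV pacing variable in place of DURAPCAD. Show exit block at maximum output separately, because output adjustment cannot prevent it.

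Report the number of patients with at least one finding over all identified patients. An exact 95% confidence interval is optional.

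The cost is SAP wording and a query on three exports already listed in SAP 5.9 (adverse_event, device_deficiency, lead_measurement). A few lead-caused events will need a short narrative. CIP 11.8 allows the SAP to be updated before database freeze or closure. Making the change there avoids a CIP amendment, which under CIP section 13 would be substantial if it affects data analysis.

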8.1.4.19 Provision of programmer data and IEGMs

During the study, programmer data containing all measurements have to be provided to the sponsor for implantation and each follow-up. To ensure that all threshold measurements are available in the programmer data, it has to be ensured that for each measured vector the pacing threshold value is actually chosen and stored. IEGMs, e.g. of tachyarrhythmia episodes, have to be actively opened once to ensure storage and export.

The programmer data and IEGMs shall be provided to the sponsor as follows:

- Delivery via ReportShare function to the Home Monitoring Service Center

Automatic export

Pre-setting of Renamic Programmer: open the 'Options' dialog in the Data Manager.

Activate the automatic upload by enabling the 'Automatic export' (3) checkbox (see Figure 10)

After implantation or FU was performed: click 'end' to close the application.

The upload will start automatically.

Or Manual export

Pre-setting of Renamic Programmer: open the 'Options' dialog in the Data Manager.

Activate the manual upload by enabling the 'HMSC export' (2) checkbox (see Figure 10)

Select one follow-up from Data Manager

Click on 'Preview' and select all checkboxes

Click on 'Export'

[figure not shown]

Figure 10: Ointerface for the export of programmer data to HMSC via ReportShare

In the exceptional case that ReportShare is not available, e.g. for organizational or technical reasons, the following alternatives may be used for delivery of programmer data and IEGMs:

- Upload to the EDC system
- Delivery via email to [REDACTED]
- Delivery via USB stick

For every export it has to be ensured that data are pseudonymized.

8.1.4.20 BIOTRONIK Home Monitoring® Data

The sponsor will collect the patient data obtained by telemetry over the period of study participation. This will include P- and R-wave sensing, pacing impedance, painless shock impedance and thresholds, periodic IEGMs and recording episodes IEGMs and further data. The observation of Home Monitoring data by the sponsor cannot be used as an emergency system. The investigator is responsible to follow-up the patients via Home Monitoring and during in-office follow-ups.

8.1.4.21 Medication Log

The medication shall be documented in the medication log. Changes or additions during study participation shall be entered in this log as well. The following data shall be entered in the log:

- Name of the medication
- Date of start and stop of application, if applicable

8.1.4.22 Adverse Events

During the course of the study, all adverse events will be reported to the sponsor and to local Ethics Committees, if required by local regulations (see also section 18.9). All adverse events will be classified according to their seriousness, the relation to the investigational devices and to the procedure. Furthermore, relation to MPP and CRT AutoAdapt, respectively, will be documented. Reporting of adverse events is required starting from the time of signature on the patient informed consent until study termination. In case serious adverse device effects (SADE) are not solved at study termination, those shall be followed up for a maximum of 4 weeks after study termination of the patient.

The definition of event classification is described in section 18.1.

8.1.4.23 Device Deficiencies

In case of a Device Deficiency (DD) the type and serial number of the affected device, a description of the deficiency and an assessment whether the deficiency could have led to a medical occurrence and/or a serious adverse device effect will be documented.

8.1.5 Equipment to be used for the assessment of variables

The following equipment is used for the assessment of the above described variables:

Device:	BIOTRONIK Acticor/Rivacor 7 series or Rivacor 5 series: VR-T, VR-T DX, DR-T, HF-T, HF-T QP
RA-lead:	Freely selectable
RV-lead:	For VR-T DX system: Plexa ProMRI S DX lead
For all other systems:	Freely selectable
LV-lead:	For HF-T system (with IS-1 connector): Freely selectable For HF-T QP system (with IS-4 connector): BIOTRONIK Sentus OTW QP lead is recommended
External programming device:	BIOTRONIK Renamic (or successors) (with UMTS-Module and software version 1801.A/4 or higher)
Programmer software:	BIOTRONIK PSW 1801.A/4 and subsequent versions
Remote monitoring tools:	BIOTRONIK CardioMessenger Smart (or successors)
Remote monitoring software:	BIOTRONIK Home Monitoring Service Center (HMSC) 3 and subsequent versions
Accessories:	BIOTRONIK Selectra LV delivery system (recommended) BIOTRONIK accessories kit (recommended)

Note: even though the choice of leads is left to the investigator, it is recommended to use the specific BIOTRONIK lead combinations that would allow the whole system (ICD + leads) to be MR conditional. Please refer to the specifications in the IFUs.

8.1.6 Replacement of subjects

During the course of the study, patients that drop out prior to any implantation attempt can be replaced as long as enrollment in the study is still ongoing. Patients who are not implanted with an investigational device and who did not come in contact with any investigational device during implantation attempt can also be replaced.

Due to replacements, the total number of enrolled patients might exceed the planned sample size.

Patients that will be lost to follow-up or prematurely terminate the study for any reason after a successful implantation will not be replaced.

8.2 Used devices and comparators

8.2.1 Description of exposure to the investigational device and/or comparator

The investigational devices used in this study are Active Implantable Medical Devices (AIMD). According to the nature of implantable devices, the devices will be implanted into the patient's body and will typically remain there for the lifetime of the device, also beyond the duration of the study.

